16.2.7 Sensitivity Analyses

If there is a more than 5% difference in the number of subjects between FAS and EFF analysis set or between PD-L1 positive FAS and PD-L1 positive EFF analysis set, tumor response based on BOR and irBOR per IERC or investigator assessment will be repeated using EFF analysis set or PD-L1 positive EFF analysis set.

CCI

[Redacted]

CCI

16.4 Pharmacokinetics and Pharmacodynamics

PK analysis will be based on the PK analysis set.

16.4.1 Missing PK Data

Concentrations below the limit of assay quantitation

PK concentrations below the lower limit of quantification (<LLOQ) are taken as zero for descriptive statistics.

PK concentrations below the lower limit of quantification (<LLOQ), which are before the last quantifiable data point, will be taken as zero for calculating the AUC of single dose profiles. Concentration below LLOQ, which occur after the last quantifiable data point, will not be considered in the calculation of the terminal first order rate constant (λ_z).

Deviations, missing concentrations and anomalous values

Concentrations reported as no result will be set to missing in summary tables.

If a PK parameter cannot be derived from a subject's concentration data, the parameter will be coded as NC (not calculated). (Note that NC values will not be generated beyond the day that a subject discontinues the treatment). For statistical analyses (i.e. analysis of variance), PK parameters coded as NC will be set to missing.

If an individual subject has a known biased estimate of a PK parameter (due for example to a deviation from the assigned dose level), this subject/value will be excluded from the descriptive statistics and instead the result will be listed in a separate table.

Relevant decisions on subject inclusion in the PK analysis set will be made before database lock in the Database Review Meeting (DRM), as far as possible. Remaining decisions will be made

prior to the performance of a descriptive analysis. PK concentrations which are erroneous due to a protocol violation (as defined in the CTP), documented handling error or analytical error (as documented in the bioanalytical report) may be excluded from the PK analysis if agreed upon prior to performing a statistical analyses. In this case the rationale for exclusion must be provided in the Clinical Trial Report (CTR). Any other PK concentrations that appear implausible to the Pharmacokineticist/PK/PD Data Analyst must not be excluded from the analysis. Any implausible data will be documented in the Clinical Trial Report (CTR). Any exclusions will be listed and flagged.

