3.4.1 Clinical Pharmacodynamics

Receptor occupancy was measured in vitro by flow cytometry on peripheral blood CD3+ T-cells after spiking of human whole blood samples from 8 healthy volunteers with avelumab over a concentration range of 0.003 to 10 µg/mL. In this assay, free receptors were measured in samples spiked over this range and compared with the amount of free receptors in the unspiked sample. A 50% receptor occupancy was observed at a drug concentration of 0.122 µg/mL ± 0.042 µg/mL (standard deviation) and a plateau indicating at least 95% receptor occupancy was reached in all donor blood samples at 1 µg/mL.

These in vitro data combined with PK data were confirmed in ex-vivo samples taken at C_{min} after the first dose (Day 15) in a small number of subjects during the initial dose escalation part of the Phase Ib Trial EMR100070-001 (n=9). For doses of 10 mg/kg, target occupancy (TO) was greater than 90% for these 4 subjects, at trough serum levels ranging between 12.69 to 26.87 µg/mL. Also, for doses of 3 mg/kg, available TO data for 2 subjects with trough levels ranging from 4.56 to 6.99 µg/mL, showed greater than 90% TO at trough exposure levels. At dose level 1 mg/kg, 2 out of 3 subjects displayed less than 90% TO at trough serum concentrations. Avelumab serum concentrations were below the quantification limit of 0.2 µg/mL in these 2 subjects.

Based on the observed avelumab serum concentrations in the EMR100070-001 Phase I clinical trial and the in vitro receptor occupancy data, trough concentrations were sufficient to achieve full target occupancy throughout the entire dosing interval in all of the subjects receiving the 10 mg/kg dose. After the 3 mg/kg dose, C_{min} were insufficient in 3 of the 13 subjects to assure full target occupancy; therefore, in order to achieve target saturation during the whole treatment period in all subjects, the dose of 10 mg/kg every 2 weeks was selected as the dose for further investigation in the Phase Ib expansion cohorts and for the subsequent clinical studies.

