16.3 Cytokine Profile

The following parameters are assessed for the cytokines profile based on SAF analysis set:

-
- Rantes, Interleukin-17, IL-6, MCP-1, IL-1beta, IL-2, IL-4, IL-5, IL-10, IL-12p70, IL-13, TNF-Alpha, IFN-Gamma.

These parameters will be summarized by visit and dose level using the following variables:

- Absolute value
- Log fold change from baseline

If values are indicated to be below the lower limit of quantification (LLOQ), they will be imputed as 0.5* LLOQ for summary analysis. If multiple measurements per time point per subject exist, a single signal value will be derived by averaging.

Log fold change from baseline (logFC) is defined as

- $\text{logFC (cytokine at time } t) = \text{log}(\text{cytokine signal at time } t) - \text{log}(\text{cytokine signal at baseline})$:

The cytokine data will be displayed graphically by dose level for each parameter:

- Boxplot of absolute value by visit (logarithmic and raw scale)
- Boxplot of log fold change from baseline by visit
- Line plot of per-subject data

The cytokine listing will be produced with relevant variables such as dose level, subject identifier, visit, parameter names and results.

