16.5 Pharmacokinetic Profile

16.5.1 Missing PK Data

All PK analyses will be based on the PK analysis set.

- **Concentrations below the limit of assay quantitation**

PK concentrations below LLOQ are taken as zero for descriptive statistics.

PK concentrations below LLOQ, which are before the last quantifiable data point, will be taken as zero for calculating the AUC of single dose profiles. Concentration below LLOQ, which occur after the last quantifiable data point, will not be considered in the calculation of the terminal first order rate constant (λ_z).

- **Deviations, missing concentrations and anomalous values**

Concentrations will be set to missing in summary tables if the value is reported as no result.

If a PK parameter cannot be derived from a subject's concentration data, the parameter will be coded as NC (not calculated). (Note that NC values will not be generated beyond the day that a subject discontinues the treatment). For statistical analyses (i.e. analysis of variance), PK parameters coded as NC will be set to missing.

If an individual subject has a known biased estimate of a PK parameter (due for example to a deviation from the assigned dose level), this subject/value will be excluded from the descriptive statistics and instead the result will be listed in a separate table.

Relevant decisions on subject inclusion in the PK analysis set will be made before database lock in the Database Review Meeting (DRM).

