- For the efficacy expansion cohorts and the urothelial carcinoma secondary cohort:
 - TTR according to RECIST 1.1, per IERC

10 Analysis Sets

The following analysis sets are defined for the dose expansion phase and summarized in Table 4:

- Screening analysis set (SCRN): all subjects who signed informed consent form (ICF).
- PK analysis set (PKAS): a subset of the safety analysis set and will include patients who have at least one post-dose concentration measurement above the lower limit of quantitation (LLOQ) for avelumab.
- Safety analysis set (SAF): all subjects who have received at least 1 dose of study treatment.
- Full analysis set (FAS): all subjects who have received at least 1 dose of study treatment.
 - PD-L1 positive (5% cut-off) FAS (urothelial carcinoma efficacy expansion cohort): all PD-L1+ subjects (defined as those with at least 5% of the tumor cells showing PD-L1 membrane staining $\geq 1+$ assessed by immunohistochemistry) who have received at least 1 dose of study treatment.
 - PD-L1 positive (1% cut-off) FAS (NSCLC cohorts): all PD-L1+ subjects (defined as those with at least 1% of the tumor cells showing PD-L1 membrane staining $\geq 1+$ assessed by immunohistochemistry) who have received at least 1 dose of study treatment.
- Efficacy analysis set (EFF, efficacy expansion cohorts): all subjects who have received at least 1 dose of study treatment and have measurable disease at baseline according to IERC assessment.
 - PD-L1 positive EFF (urothelial carcinoma efficacy expansion cohort): all PD-L1+ subjects (defined as those with at least 5% of the tumor cells showing PD-L1 staining $\geq 1+$ assessed by immunohistochemistry) who have received at least 1 dose of study treatment and have measurable disease at baseline according to IERC assessment.
- Efficacy analysis set (primary and secondary expansion cohorts): all subjects who have received at least 1 dose of study treatment and have measurable disease at baseline according to investigator assessment.

The definition of the SAF and the FAS are identical in this non-randomized study; the SAF will be used for the safety analysis and the FAS will be used for efficacy analysis. The PD-L1 positive FAS will be the primary analysis population for the primary endpoint of BOR by IERC in the urothelial carcinoma efficacy expansion cohort, whereas for the other efficacy expansion cohorts the primary analysis population will be the FAS.

Table 4 Summary of Analysis Sets and Associated Analyses

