16.4.2 Descriptive PK Analysis

Avelumab serum concentrations will be provided in listings and descriptively summarized by day and nominal time using the number of non-missing observations (N), arithmetic mean (Mean), standard deviation (SD), coefficient of variation (CV%), minimum (Min), median (Median) and maximum (Max). The pre-dose samples will be considered as if they had been taken simultaneously with the administration.

PK concentrations at the end of each infusion (C_{EOI}) and trough concentrations (C_{trough} - concentration at the end of a dosing interval) will be summarized descriptively by nominal day on scheduled visits for all tumor types. Descriptive statistics for C_{trough} and C_{EOI} will additionally show the geometric mean (GeoMean), the geometric coefficient of variation (GeoCV) and the 95% confidence interval for the GeoMean (Lower CI 95% GeoMean, Upper CI 95% GeoMean).

Descriptive statistics of PK concentration data will be calculated using values with the same precision as the source data, and rounded for reporting purposes only. The following conventions will be applied when reporting descriptive statistics of PK/PD concentration data:

Mean, Min, Median, Max:	3 significant digits
SD:	4 significant digits
CV%:	1 decimal place

The following conventions will be applied when reporting descriptive statistics of C_{EOI} and C_{trough} data:

Mean, Min, Median, Max, GeoMean, 95% CI:	3 significant digits
SD:	4 significant digits
CV%, GeoCV%:	1 decimal place

Individual C_{trough} and C_{EOI} values will be plotted against actual time points on a linear scale, for all subjects by group (cohort and dose level). Arithmetic mean $C_{\text{trough}} \pm \text{SD}$ and arithmetic mean $C_{\text{EOI}} \pm \text{SD}$ will also be plotted by group (cohort and dose level), on a linear scale.

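### Setting concentrations below LLOQ to zero makes the geometric trough statistics zero or undefined, and neither SAP states a separate rule for them

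*SAP*

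**What the plan says.** Expansion SAP, Section 16.4.1: "PK concentrations below the lower limit of quantification (<LLOQ) are taken as zero for descriptive statistics". No exception is made. In Section 16.4.2, concentrations get arithmetic summaries plus N, defined as the count of non-missing observations. The summaries of C_trough and C_EOI "will additionally show the geometric mean (GeoMean), the geometric coefficient of variation (GeoCV) and the 95% confidence interval for the GeoMean".

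The PK analysis set (expansion SAP, Section 10) needs only "at least one post-dose concentration measurement above the lower limit of quantitation (LLOQ) for avelumab". A subject with one quantifiable sample therefore stays in, along with any trough below LLOQ at another visit.

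The dose-escalation SAP, Section 16.5.1, has the same rule: "PK concentrations below LLOQ are taken as zero for descriptive statistics". Its Section 16.5.2 asks for the geometric mean, geometric CV and CI for PK parameters, and Section 16.5.3 lists Cmin as one of those parameters.

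For cytokines, the dose-escalation SAP (Section 16.3) uses a different convention: "If values are indicated to be below the lower limit of quantification (LLOQ), they will be imputed as 0.5* LLOQ for summary analysis".

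**The concern.** A geometric mean, its CV and its interval are all computed from logarithms, and the logarithm of zero does not exist. The two instructions cannot both be carried out at a visit where any trough is below LLOQ. Neither SAP supplies an exclusion, a substitution, a rule to leave the cell blank, or a count of affected values. The not-calculated code in the missing-data sections covers a parameter that cannot be derived from one subject's data, not a summary statistic spoiled by zeros.

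The choice would then fall to whoever programs the table. Keeping the zeros gives an uninformative cell. Dropping them removes the lowest exposures, which are not a random subset. That bears on the secondary objective of relating immunogenicity to exposure, because loss of exposure is what such values would show.

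These troughs do occur. For two of the three subjects described at 1 mg/kg, Protocol Section 3.4.1 reports: "Avelumab serum concentrations were below the quantification limit of 0.2" µg/mL. Protocol Section 3.3 describes loss of quantifiable exposure in at least one subject with anti-drug antibodies at 3 mg/kg.

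**Working it through.** The plan gives no figure to reproduce, so the check applies the stated rules to plausible data.

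**Inputs from the documents**
- LLOQ 0.2 µg/mL (Protocol 3.4.1).
- Median first-cycle trough at 10 mg/kg: 20 µg/mL, n = 256 (Protocol 3.3).
- 2 of 3 subjects below LLOQ at trough at 1 mg/kg (Protocol 3.4.1).

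**Assumptions, not in the documents**
- The median of 20 also serves as the geometric mean of the quantifiable troughs.
- Troughs are log-normal with a geometric CV of 50%.
- The share of troughs below LLOQ ranges from 1 in 256 (0.4%) to 5%.

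**Formulas.** With m and s the mean and SD of ln x: GeoMean = exp(m); GeoCV = 100·√(exp(s²) − 1); 95% CI = exp(m ± t·s/√n).

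**Zeros kept, as written.** With 1, 3 or 13 zeros among 256 values, GeoMean = 0 and GeoCV and CI are undefined each time. Arithmetic summaries survive: with one zero the mean is 22.3 and the median 20.0.

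**Zeros dropped.** GeoMean stays at 20.0 and GeoCV at 50% however many values are below LLOQ. The statistics then rest on 255, 253 or 243 values while N reads 256.

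**Size of the difference.** If a fraction q is placed at value c and the rest have geometric mean 20, the overall GeoMean is 20 × (c/20)^q. With c = LLOQ/2 = 0.1:

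| q | GeoMean with LLOQ/2 | Dropped-value result (20) is higher by |
|---|---|---|
| 1/256 (0.4%) | 20 × 0.005^0.0039 = 19.6 | 2% |
| 1% | 20 × 0.005^0.01 = 19.0 | 5% |
| 3% | 20 × 0.005^0.03 = 17.1 | 17% |
| 5% | 20 × 0.005^0.05 = 15.3 | 30% |

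Placing these values at the LLOQ itself (c = 0.2), the highest they could be, gives 17.4 at 3% and 15.9 at 5%. The dropped-value result is then 15% and 26% higher.

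**Side effect of LLOQ/2.** GeoCV rises from 50% to 63% with 1 value below LLOQ, to 85% with 3 and to 195% with 13. The value 0.1 lies far from the bulk of the data on the log scale.

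**The documented 1 mg/kg case.** With two zeros of three, GeoMean = 0. With the zeros dropped, n = 1 and neither GeoCV nor CI can be computed.

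**The case against.** The strongest reply is that no decision in the documents uses a geometric mean trough. A reader might infer that dose selection or the target-occupancy argument is compromised, but the documents do not support that. Protocol 3.4.1 chose 10 mg/kg from individual troughs and occupancy (3 of 13 subjects insufficient at 3 mg/kg), and Protocol 3.3 reports medians, which zeros leave defined. Exposure-response work (expansion SAP 16.4.4) uses individual exposures, and population PK has its own plan (16.4.3). This stands in full.

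Second, the documented cases are at 1 and 3 mg/kg, whereas the expansion dose is 10 mg/kg. There the median trough is 20/0.2 = 100 times the LLOQ. The lowest steady-state trough given in Protocol 3.5.1 for that regimen, 4.2 µg/mL, is 21 times the LLOQ. A reader might infer that troughs below LLOQ are common in expansion, but no such case is documented and no rate is given. This stands as to frequency. It does not remove the conflict, since one value at a visit is enough, and expansion SAP 16.5.1 itself provides for avelumab concentrations below LLOQ in a plot.

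Third, dose-escalation SAP 16.5.2 summarises its trough tables with arithmetic statistics and reserves geometric ones for PK parameters. That is a fair reading of the trough tables. Because Cmin is also listed as a PK parameter, the clash returns by that route.

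Fourth, dropping would not be wholly hidden: a minimum of 0 would appear in the same table, and individual values are listed and plotted. That would reveal that some value was below LLOQ, but not how many, nor that the geometric columns leave them out. Nothing in the documents says that software will drop zeros, so this is one possible handling and not a prediction.

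**Conclusion.** The point holds as a genuine but limited inconsistency. Both SAPs set values below LLOQ to zero for descriptive statistics and also require log-scale statistics for troughs, directly in the expansion SAP and through Cmin in the dose-escalation SAP. Nothing else in either document resolves it. Where no trough is below LLOQ, the statistics are well defined.

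The 2% to 30% range rests on assumed rates of 0.4% to 5%, on treating the median of 20 µg/mL as a geometric mean, and on LLOQ/2 as the comparator. It shows sensitivity and does not estimate what the trial will find. At 10 mg/kg the lower end is more plausible, because troughs lie so far above the LLOQ. C_EOI falls under the same rule but is unlikely to be affected.

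The consequence is confined to secondary descriptive PK tables. Dose selection, population PK and the primary endpoint of confirmed best overall response are untouched.

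**What to change.** In both SAPs, limit the zero rule to arithmetic summaries and state a separate rule for the geometric mean, geometric CV and CI before the tables are produced. Two workable choices are LLOQ/2, which the dose-escalation SAP already uses for cytokines, or reporting the geometric statistics as not calculated whenever a value below LLOQ is present. Under either choice, report the number of values below LLOQ at each visit and the number of values used in each geometric statistic.

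The cost is a sentence in each SAP and an extra line or two in the trough tables. The drawback of LLOQ/2 is the inflated geometric CV when troughs lie far above the LLOQ, so the count must stand beside it. The drawback of not calculating is an empty cell at the visits concerned.

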16.4.2 Descriptive PK Analysis

Avelumab serum concentrations will be provided in listings and descriptively summarized by day and nominal time using the number of non-missing observations (N), arithmetic mean (Mean), standard deviation (SD), coefficient of variation (CV%), minimum (Min), median (Median) and maximum (Max). The pre-dose samples will be considered as if they had been taken simultaneously with the administration.

PK concentrations at the end of each infusion (C_{EOI}) and trough concentrations (C_{trough} - concentration at the end of a dosing interval) will be summarized descriptively by nominal day on scheduled visits for all tumor types. Descriptive statistics for C_{trough} and C_{EOI} will additionally show the geometric mean (GeoMean), the geometric coefficient of variation (GeoCV) and the 95% confidence interval for the GeoMean (Lower CI 95% GeoMean, Upper CI 95% GeoMean).

Descriptive statistics of PK concentration data will be calculated using values with the same precision as the source data, and rounded for reporting purposes only. The following conventions will be applied when reporting descriptive statistics of PK/PD concentration data:

Mean, Min, Median, Max:	3 significant digits
SD:	4 significant digits
CV%:	1 decimal place

The following conventions will be applied when reporting descriptive statistics of C_{EOI} and C_{trough} data:

Mean, Min, Median, Max, GeoMean, 95% CI:	3 significant digits
SD:	4 significant digits
CV%, GeoCV%:	1 decimal place

Individual C_{trough} and C_{EOI} values will be plotted against actual time points on a linear scale, for all subjects by group (cohort and dose level). Arithmetic mean $C_{\text{trough}} \pm \text{SD}$ and arithmetic mean $C_{\text{EOI}} \pm \text{SD}$ will also be plotted by group (cohort and dose level), on a linear scale.

16.4.3 Population Pharmacokinetic Analysis

Sampled PK profiles from study EMR100070-001 will be analyzed jointly with data from other studies by non-linear mixed effect approach, in order to describe the PK concentration time profile followed by multiple dose infusion of avelumab, to identify covariates explaining (part of) the between patient PK variability and to estimate the residual PK inter-individual variability. The PK analysis set will be used. More details will be given in a separate Data Analysis Plan for Population Pharmacokinetic Analysis. The results will be reported separately.

16.4.4 Relation of Pharmacokinetics to Efficacy in Urothelial Carcinoma Cohorts

The exposure-response analysis will include subjects with urothelial carcinoma from the Full Analysis Set (secondary cohort of urothelial carcinoma and efficacy expansion cohort of urothelial carcinoma). The analyses will be based on a data cut-off for the urothelial carcinoma efficacy expansion cohort, i.e. 6 months after start of treatment of the 109th subject.

The objectives of this exploratory population exposure response analysis are: To assess the relationships between objective response (OR), overall survival (OS), and progression-free survival (PFS) with avelumab exposure (e.g., single dose trough concentration ($C_{\text{trough_sd}}$), steady-state $C_{\text{trough_ss}}$), and steady-state AUC_{ss}, and single dose AUC_{sd}) in the presence of other relevant covariates.

For OR, the patients will be classified as responder or non-responder based on best overall response (BOR) according to RECIST 1.1 following IERC assessment (responder: CR and PR; non-responder: stable disease [SD], progressive disease [PD], non-evaluable [NE]). OS and PFS will be reported in months.

Population PK parameters, as determined by the final population modeling analysis will be used to derive individual exposure metrics including, but are not limited to $C_{\text{trough_sd}}$, $C_{\text{trough_ss}}$, AUC_{ss} and AUC_{sd}. In addition, observed concentration values (i.e. observed single dose C_{trough} , observed steady-state C_{trough}) may be used to represent exposures.

Multivariable regression models will be employed with a stepwise variable selection process. The covariates will be inserted subsequently to the regression model starting with the covariate linked to the smallest p value (corresponding to the Wald chi-square statistic, given the covariates degrees-of-freedom) not yet included to the model if the corresponding p value is below or equal the inclusion threshold of 15%. After each forward step (i.e. inclusion of a new covariate) the new larger regression model passes a backward step, in which subsequently all covariates are excluded (starting with the covariate linked to the highest p value) if their Wald chi-square p-values lie above the exclusion threshold of 40%. The stepwise procedure stops when no further effect can be added or the previously added effect in the forward step was removed in the next backward step.

The interpretation and final inclusion of the covariate(s) in the final model will depend on biological plausibility, dataset attributes and clinical significance of the covariate in question.

Covariates to be tested consider potential prognostic factors including the following in Table 8:

Table 8 Table of potential covariates for regression models

Category	Covariates
Demographics	race, sex, age, baseline body weight
Prior Treatments	Prior radiotherapy (Y/N), Number of prior anti-cancer drug therapies, Prior adjuvant therapy
Safety laboratory information at baseline	Albumin, alkaline phosphatase, bilirubin, alanine aminotransferase, aspartate aminotransferase, platelet count, lactate dehydrogenase at baseline, eGFR*, hemoglobin
Disease-related laboratory values	PD-L1 status
Disease Status/Treatment	Baseline ECOG Status (0/1/2) Concomitant medication of Corticosteroids for systemic use (Y/N) Metastatic disease** at enrolment (study entry) – liver metastasis, other metastasis, no metastasis Number of non-target lesions at baseline Tumor burden at baseline (mm) Tumor sub-site (Lower tract / Upper tract) Eligibility of platinum-based therapy *** (Y/N)

*eGFR is calculated as follows:

$$eGFR=32788*CREAT^{**}(-1.154)*AGE^{**}(-0.203) + SEX*0.742+MRACE*1.210$$

where CREAT is serum creatinine (µmol/L), AGE is age (years), Sex is a flag for sex (0 for males, 1 for females) and MRACE is a flag for race (1 for Black or African American, 0 otherwise). $CREAT(mg/dL)*88.4=CREAT(\mu mol/L)$

** as evaluated by local or central tumor assessments

*** Subjects are considered eligible for platinum-based therapy in case they receive cisplatin as a prior anti-cancer treatment.

Missing time-invariant categorical covariates will be set to be a separate category distinct from other categories. If the percentage of missing values is below 10%, the missing values should be imputed based on modeler’s decision to balance the distribution of the categorical covariate. Missing time-invariant continuous covariates will be to the population median or excluded from the analysis if the percentage of missing values is equal or larger than 25%.

The exposure-response relationship for BOR will be performed using R or NONMEM 7.3. Exposure-response calculations regarding PFS and OS will be performed using the software SAS 9.3 or R.

